The Efficacy and Safety of Silodosin Singly or Combined with Ningmitai Capsules in the Treatment of Benign Prostatic Hyperplasia (BPH) Complicated with Lower Urinary Tract Symptoms (LUTS) —A Multicenter, Prospective, Randomized, Doubleblind, Positive Controlled Study

Date: September 8, 2022

Research Proposal Summary

Scheme number	NM-22-A-001-YJ-001					
Scheme name	The Efficacy and Safety of Silodosin Capsules Singly or Combined with Ningmitai Capsules in the Treatment of Benign Prostatic Hyperplasia					
Version number/date	Version 1.0, December2, 2021					
sponsor	Shanghai Haitian Pharmaceutical Technology Development Co., Ltd.					
Clinical trial staging	Post-marketing clinical re-evaluation					
test drug	Ningmitai Capsules (Ningmitai [®] , Z20025442), each 0.38g, was produced by Guiyang Xintian Pharmaceutical Co., Ltd.					
	Silodosin Capsules (Qianweitai®, H20213612), each 4mg, was produced by Shanghai Huilun Pharmaceutical Co., Ltd.					
	Tamsulosin Hydrochloride Sustained Release Capsules(H20000681), each0.2mg, was produced by Astellas Pharma Inc.					
	Placebo, Ningmitai capsule simulator, each0.38g, was produced by Guiyang Xintian Pharmaceutical Co., Ltd.					
Indications	Benign Prostatic Hyperplasia with Lower Urinary Tract Symptom					
Test purposes	1.To evaluate the efficacy and safety of Silodosin Capsules alone versus Tamsulosin Hydrochloride Sustained Release Capsules in the treatment of BPH with lower urinary tract symptoms.					
	2.To evaluate the efficacy and safety of Ningmitai Capsules combination with Silodosin Capsules versus Silodosin Capsules alone in the treatment of BPH with lower urinary tract symptoms.					
Research design	A multicenter, prospective, randomized, controlled clinical trial design					
total number	It is planned to complete 312 cases (considering the 20% dropout rate)					
number of research	8					

centers					
Study period	6 months				
research	Diagnostic criteria:				
object	1. Male Subjects aged 60 ~ 80 years, clinically diagnosed as benign prostatic hyperplasia.				
	2. Has an IPSS score ≥ 8 points at Screening and Baseline.				
	3. Has a $4 \le Q_{max} \le 15$ ml/s when urination volume > 150 ml.				
	4. Has a prostate volume (PV) \geq 30 ml by ultrasound examination.				
	5. Subjects who can read, understand, and complete the research questionnaire.				
	6. Subjects willing to participate voluntarily in this clinical trial, give informed consent and sign				
	informed consent.				
	Exclusion criteria: 1. Subjects with prostate cancer or other malignant tumors.				
	2. Subjects have serum tPSA > 10ng/ml , or $4 \le \text{tPSA} \le 10 \text{ng/ml}$ while fPSA/tPSA < 0.16 times.				
	3. Subjects suffered from other diseases causing dysuria, such as bladder neck spasm, urethral				
	stricture, neurogenic bladder dysfunction, etc.				
	4. Subjects have suffered from acute urinary retention, or complicated with gross hematuria,				
	urinary tract infection, bladder stones, secondary upper urinary tract hydronephrosis, urinary				
	incontinence, renal insufficiency and other subjects that researchers believe meet the surgical				
	indications.				
	5. Subjects have undergone prostate surgery, microwave therapy, urethral dilatation or acute				
	urinary retention catheterization or other invasive procedures.				
	6. Subjects have residual urine volume (PVR) > 100ml, or those who may have urinary retention				
	and need catheterization.				
	7. Subjects who took α receptor blockers, traditional Chinese Medicine or botanical drugs for				
	treating BPH within two weeks before participating this clinical trial.				
	8. Subjects who take 5α reductase inhibitor or other antiandrogen therapy drugs within half a year				
	before participating this clinical trial.				
	9. Subjects who need to take drugs prohibited in this study or adopt prohibited treatment methods				
	during treatment.				
	10. Subjects who Complicated with severe cardiovascular and cerebrovascular diseases, respiratory				
	diseases, blood diseases, liver, and kidney diseases.				
	11. There are significant abnormalities in clinical or laboratory examination indexes of patients,				

such as ALT and AST \geq 2.5 times of the upper limit of reference value, creatinine (Scr) > 1.5 times of the upper limit of reference value, or poor blood glucose control (fasting blood glucose FPG \geq 10 mmol/L).

- 12. Subjects who are allergic to the drugs or ingredients used in the test definitely.
- 13. Any other Subjects in the opinion of researchers is not suitable for inclusion.

Trial grouping and

According to the random sequence generated by computer, eligible patients were randomly assigned to three groups according to 1: 1: 1.

medication

Group A: Tamsulosin combined with Ningmitai Capsules placebo. Oral Tamsulosin Hydrochloride Capsules (each 0.2mg), 1 capsule per time, 1 time a day. Oral Ningmitai Capsules placebo (each 0.38g), 4 capsules per time, 3 times a day. Continuous medication for 12 weeks.

Group B: Silodosin Capsules combined with Ningmitai Capsules placebo. Oral Silodosin Capsules (each 4mg), 1 capsule per time, 2 times a day. Oral Ningmitai Capsules placebo (each 0.38g), 4 capsules per time, 3 times a day. Continuous medication for 12 weeks.

Group C: Silodosin Capsules combined with Ningmitai Capsules. Oral Silodosin Capsules (each 4mg), 1 capsule per time, 2 times a day. Oral Ningmitai Capsules (each 0.38g), 4 capsules per time, 3 times a day. Continuous medication for 12 weeks.

Combined medication

Combination drugs banned during the study:

- (1) CYP3A4 inhibitors (eg. Ketoconazole, Clarithromycin, Itraconazole, Ritobuvir)
- (2) Other α-receptor blockers besides this study and other drugs with therapeutic effects on BPH include 5-α reductase inhibitors, phosphodiesterase type 5 (PDE-5) inhibitors, M receptor blockers, β3 receptor agonists, botanical drugs or traditional Chinese medicines, etc.

Combination drugs used with caution during the study:

- (1) Strong inhibitors of CYP2D6 (such as Paroxetine) may lead to a significant increase in exposure to Tamsulosin.
- (2) Potential P-glycoprotein (P-gp) inhibitors (such as Cyclosporin), in vitro studies have shown that Silodosin is a P-gp substrate, and the inhibition of P-gp may lead to an increase in the blood concentration of Silodosin.
- (3) Antihypertensive drugs, there is a decline in blood pressure regulation ability when standing up and pay close attention to blood pressure changes when combined with α -receptor blockers.
- (4) Drugs that may induce or aggravate urinary retention, such as Anticholinergic Atropine, Antiallergic Chlorpheniramine, Antidepressant Imipramine, and ready-for-use traditional Chinese

medicine or decoction containing ephedra.

Concomitant drugs allowed during the study period:

If the subjects have basic diseases and need to take drugs for a long time, and they are not prohibited drugs in this study, they can continue to use them during the study period.

If the subject has adverse reactions, it is up to the researcher to decide whether to use symptomatic treatment drugs.

All drugs used at the same time should be recorded and explained in detail on CRF table.

Treatment and

follow-up

Course of treatment: 12 weeks

Visit points: screening period, days -28 to 0), after 1 week of treatment (day 7 ± 2), after 2 weeks of treatment (day 14 ± 3), after 4 weeks of treatment (day 28 ± 5), after 8 weeks of treatment (day 56 ± 7), after 12 weeks of treatment (day 84 ± 10).

Research steps

This trial is divided into two stages: screening period, treatment period and follow-up period.

Screening period (days -28 to 0): After signing the informed consent form, the subjects entered the screening period, and made a 24-hour urination diary and screening examination.

Treatment and Follow-up period: eligible patients were randomly assigned to three groups according to 1: 1: 1 and received Tamsulosin + placebo, Silodosin + placebo or Silodosin + Ningmitai for 12 weeks. During the treatment period, the subjects' diaries were recorded according to the requirements of the scheme, and they were followed up at 1 week (7 ± 2 days), 2 weeks (14 ± 3), 4 weeks (28 ± 5 days), 8 weeks (56 ± 7 days) and 12 weeks (84 ± 10 days). During the visit, relevant scale scores and laboratory examinations were performed, and the occurrence of adverse events during the follow-up was recorded to evaluate the safety.

study endpoint

Primary endpoint:

International Prostate Symptom Score (IPSS), Changes of scores at the 12th week of treatment compared to the baseline scores.

Secondary endpoints:

1.IPSS Score

- ①changes of IPSS total score: Changes of IPSS scores at 1, 2, 4 and 8 weeks after treatment compared with baseline scores
- ②Proportion of patients with IPSS total score severity decreased by at least one grade at 12 weeks
- ③IPSS sub-score: IPSS Stimulation Score at 1, 2, 4, 8, 12 weeks (Sum of Question 2, 4, 7) and

Changes of IPSS obstruction score (sum of question 1, 3, 5, 6) compared with baseline.

- 2.Quality of life (QoL) score: Changes in scores at 4, 8 and 12 weeks of treatment compared with baseline
- 3. Maximum urinary flow rate (Q_{max})

The change of Q_{max} at 12 weeks of treatment compared with baseline.

4. Patient response rate

Patient response rate is defined as the proportion of patients whose IPSS total score decreased by \geq 25% and Q_{max} .

increased by $\geq 30\%$ compared with baseline value after treatment.

5. Residual urine volume (PVR)

Changes of PVR at 12 weeks of treatment compared with baseline.

6. Prostate specific antigen (PSA)

Changes of PSA at 12 weeks of treatment compared with baseline.

7. Prostate volume (PV)

Changes of PV at 12 weeks of treatment compared with baseline.

8. Proportion of patients with BPH clinical progression

Clinical progress is defined as the first occurrence of one of the following two conditions during the trial:

- ① Acute urinary retention (AUR).
- 2 Clinical diagnosis requires surgical treatment of BPH.

Subgroup analysis:

Patients were grouped according to the following conditions of subjects at baseline, and the therapeutic effect of curative effect indicators was evaluated among different subgroups to determine whether the therapeutic effect was consistent among subgroups:

- ①The scores of IPSS were moderate (8-19) and severe (20-35);
- ②Routine examination of EPS (EPS leukocytes > 4HP or < 4HP. If EPS is not collected after prostate massage, it is not advisable to repeat massage for many times, and it is recommended to take urine after prostate massage for analysis.).
- ③Symptoms of chronic prostatitis (NIH-CPSI pain score ≥ 4 and < 4)

security	The incidence of adverse drug events/reactions was calculated according to the following				
indicators	indicators:				
	1.Vital signs: Blood pressure, heart rate				
	2.Laboratory examination index: Blood routine, Urine routine, liver function (ALT, AST, ALP) and				
	renal function (BUN, Scr).				
	3.Possible adverse drug events/reactions.

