The Efficacy and Safety of Silodosin Singly or Combined with Ningmitai Capsules in the Treatment of Benign Prostatic Hyperplasia (BPH) Complicated with Lower Urinary Tract Symptoms (LUTS) —A Multicenter, Prospective, Randomized, Double-blind, Positive Controlled Study

Date: September 8, 2022

Statistical analysis Plan

1.Statistical analysis of population:

- (1) **FAS:** According to the basic principle of intentionality analysis (ITT), all the randomized subjects with more than one medication record and effectiveness evaluation were included in the full analysis set. The total analysis set is the main validity evaluation population of this study.
- (2) **PPS:** Include all subjects who have completed the treatment stipulated in the scheme or have not seriously violated the trial scheme. The exact definition of the serious violation scheme will be finalized during the data review. PPS is the secondary analysis population of validity, but if its results are inconsistent with the full analysis set, it is necessary to analyze the inconsistent results in detail.
- (3) **SS:** Defined as all subjects who were randomized and received at least one trial drug treatment. The safety analysis set is the safety evaluation population of this study.

2.Statistical analysis method:

- (1) **General principle:** All statistical analysis shall be processed by SPSS 23.0 and above statistical software, and shall be carried out according to the pre-established statistical analysis plan. Measurement data are described by mean, standard deviation, median, quartile, maximum and minimum. The counting data are described by frequency and percentage. After 12 weeks of treatment, the changes of IPSS scores between Tamsulosin + placebo group and Silodosin + placebo group were compared by non-inferior test, while the changes of IPSS scores between Ningmitai + Silodosin group and Silodosin + placebo group were compared by superior test, and the test levels were $\alpha = 0.025$ (unilateral). Other hypotheses were tested by two-side test with a test level of $\alpha=0.05$, and the secondary index was adjusted by Bonferroni method with a test level of $\alpha=0.0167$.

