- (2) **Balance analysis of baseline value:** Comparability analysis of demographic characteristics, general situation and baseline situation (before treatment) of the two groups of data. Among them, t test or Wilcoxon rank sum test was used for measurement data and grade data, and χ^2 test or Fisher exact probability method was used for classification data.
- (3) **Effectiveness analysis:** Conducted in FAS and PPS at the same time.

① **Main endpoint indicators:** After 12 weeks of treatment, the difference of IPSS score decline and 97.5% CI of the three groups were calculated. If the lower limit of unilateral 97.5% confidence interval of the difference of IPSS score decline between Silodosin + placebo group and Tamsulosin + placebo group is greater than the non-inferiority threshold of 1 (-1 point), then "Silodosin + placebo" is not inferior to "Tamsulosin + placebo" group. If the lower limit of unilateral 97.5% confidence interval of the difference between the IPSS scores of Silodosin + Ningmitai group and Silodosin + placebo group is greater than the superior effect threshold of 2 (0 points), then "Silodosin + Ningmitai" is superior to "Silodosin +

placebo". Subgroup analysis was considered according to whether the NIH-CPSI pain score was ≥ 4 before treatment and the severity of IPSS total score.

②Secondary endpoint index: The changes of IPSS scores, IPSS sub-scores and QoL scores were compared between groups at 1, 2, 4, 8 and 12 weeks after treatment. The changes of Q_{max} , PVR, serum PSA and prostate volume were compared between groups by single factor analysis of variance or Wilcoxon rank sum test. Bonferroni method was used to adjust the test $\alpha = 0.0167$. The clinical progression curve of BPH was drawn by Kaplan-Meier; COX regression model was used to compare the factors affecting the clinical progression of BPH. The proportion of patients with IPSS total score decreased in severity was compared between groups by χ^2 test or Fisher exact probability method.

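### The primary IPSS comparison adjusts for no pre-treatment IPSS: valid, but it gives up precision on both primary contrasts

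*Protocol*

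**What the plan says.** - **Eligibility** (Protocol, Research Proposal Summary, research object, criterion 2; repeated in the SAP document): "Has an IPSS score ≥ 8 points at Screening and Baseline". Two pre-treatment occasions are named for the primary measure.
- **Visits** (Protocol, Treatment and follow-up): "Visit points: screening period, days -28 to 0". This is the only pre-treatment entry. No separate baseline visit is listed and baseline is not defined.
- **Primary endpoint** (Protocol, study endpoint): "Changes of scores at the 12th week of treatment compared to the baseline scores".
- **Primary analysis** (SAP 2(3)①): "the difference of IPSS score decline and 97.5% CI of the three groups were calculated". No model and no covariate is named, so I read it as an unadjusted comparison of declines.
- **Decision rules** (SAP 2(3)①): for B-A, the lower limit "is greater than the non-inferiority threshold of 1 (-1 point"); for C-B, it "is greater than the superior effect threshold of 2 (0 points"). I take these thresholds as -1 and 0. SAP 2(1) sets one-sided 0.025 for each.
- **Size** (Protocol, total number): "It is planned to complete 312 cases (considering the 20% dropout rate").

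**The concern.** Men who start with a high score usually have more room to fall. A comparison of raw declines leaves that predictable variation in the error term. It also subtracts a single noisy self-report from another. A model that includes the pre-treatment score removes part of this variation and estimates the same treatment difference.

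Both primary decisions turn on where a confidence limit falls, and the non-inferiority rule allows only 1 point. A wider interval than necessary raises the chance that a silodosin arm no worse than tamsulosin misses the -1 limit, or that a real benefit of the combination fails to clear 0. The data that would narrow the interval are already required for eligibility and for the endpoint itself.

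**Working it through.** **1. The plan's own figure.** 312 / 3 = 104 per arm. Only the dropout step can be checked: 83 / (1 - 0.2) = 103.75, rounded up to 104, and 86 × 1.2 = 103.2, also rounded up to 104. Both lead to 312. No SD, effect, power or correlation is given, so the rest cannot be rebuilt. Everything below uses assumed values.

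**2. Notation.** Week-12, baseline and screening scores have a common variance, set to 1. ρ is the baseline to week-12 correlation, ρs the screening to week-12 correlation, and r the screening to baseline correlation.

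**3. Adjusting for baseline alone.** Planned change score: variance 2 - 2ρ. Linear model with baseline: 1 - ρ². The cut is 1 - (1 - ρ²)/(2 - 2ρ) = (1 - ρ)/2.

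| ρ | Change score | Baseline-adjusted | Variance cut | Interval narrower by |
|---|---|---|---|---|
| 0.5 | 1.00 | 0.75 | 25% | 13.4% |
| 0.6 | 0.80 | 0.64 | 20% | 10.6% |
| 0.7 | 0.60 | 0.51 | 15% | 7.8% |

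With unequal SDs the saving is (SD of baseline - ρ × SD at week 12)². It is never negative, but it shrinks if baseline scores are less spread out than week-12 scores, as an entry floor of 8 could cause.

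**4. Adding a distinct screening score to that model.** If ρs = ρ, the residual variance is 1 - 2ρ²/(1 + r). For r = 0.7 and ρ = 0.5: 1 - 0.5/1.7 = 0.706, and 1 - 0.706/0.75 = 5.9%. Further cut on top of step 3:

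| r | ρ = 0.5 | ρ = 0.6 | ρ = 0.7 |
|---|---|---|---|
| 0.7 | 5.9% | 9.9% | 17.0% |
| 0.8 | 3.7% | 6.2% | 10.7% |
| 0.9 | 1.8% | 3.0% | 5.1% |
| 1.0 (same reading) | 0% | 0% | 0% |

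If screening predicts week 12 less well than baseline does, R² = (ρ² + ρs² - 2ρρs r)/(1 - r²):

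- ρ = 0.6, ρs = 0.5, r = 0.8: R² = 0.13/0.36 = 0.361; residual 0.639 against 0.640, a cut of 0.2%.
- ρ = 0.5, ρs = 0.4, r = 0.7: R² = 0.13/0.51 = 0.255; residual 0.745 against 0.750, a cut of 0.7%.
- ρ = 0.7, ρs = 0.6, r = 0.8: R² = 0.178/0.36 = 0.494; residual 0.506 against 0.510, a cut of 0.9%.

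**5. Using the mean of the two scores as the only covariate.** With change from baseline as outcome, the residual variance is 1 - 2ρ²/(1 + r) + (1 - r)/2. At r = 0.7, ρ = 0.5: 1 - 0.294 + 0.150 = 0.856, against 0.750 for baseline alone. At r = 0.8, ρ = 0.6 it is 0.700 against 0.640; at r = ρ = 0.7, 0.574 against 0.510. This form is less precise than step 3 each time.

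**6. What the step 3 cut could mean for power.** Assume 83 evaluable per arm, a true B-A difference of 0 and the margin of 1. Power = Φ(1/(SD × √(2/83)) - 1.96), where the SD of the planned change score is assumed and is multiplied by √(1 - cut).

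| SD of change | As planned | 15% cut | 25% cut |
|---|---|---|---|
| 2.3 | 80% | 86% | 90% |
| 3 | 57% | 64% | 70% |
| 5 | 25% | 29% | 32% |

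The same figures hold for C-B if the true advantage is 1 point.

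**The case against.** The best defence is that nothing here is an error. Randomisation makes the raw comparison of declines unbiased, and a single baseline is common practice. That stands: this is a matter of efficiency only.

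A reader might infer from criterion 2 that every man gives two distinct pre-treatment readings and that the plan discards one at a known cost in precision. The documents do not support this. The schedule has one pre-treatment window, day 0 lies inside it, no gap between the two scores is required, and one questionnaire could serve both purposes. In that case the two covariates coincide and the second adds nothing.

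Even if the readings are distinct, they may not be equally informative. Exclusion 7 counts two weeks back from an undefined point of participation, while screening may begin at day -28. Some screening scores might therefore reflect an earlier BPH drug. The larger entries in the step 4 grid assume that this does not matter, and the 17% entry also needs the correlation across 12 weeks of treatment to equal the correlation between two pre-treatment readings.

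A reader might also take the average of the two scores to be an interchangeable covariate. Step 5 shows that it is not when the outcome is change from the single baseline.

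These objections shrink the part due to the screening score, possibly to nothing. They do not touch the gain from baseline adjustment, which needs only a score the endpoint already uses.

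**Conclusion.** The point holds as a low-cost improvement in precision. The primary analysis uses no pre-treatment IPSS as a covariate and so yields wider intervals than necessary for both contrasts. Most of the recoverable precision comes from the baseline score: about 25% to 15% of variance for a pre-post correlation of 0.5 to 0.7, if variances are equal. The screening score is a possible extra, worth about 0% to 10% of the remaining variance in most of the cases examined and nothing if it is not a separate reading. None of the correlations or SDs is in the documents, so the direction is firm in large samples and the size is conditional. The plan's validity is not in question.

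**What to change.** In SAP 2(3)①, before unblinding:

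1. Define baseline as the last IPSS before the first dose, and state when the screening and baseline scores are each taken.
2. State that week-12 change in IPSS is analysed in a linear model with arm and baseline IPSS, and that the B-A and C-B differences and their lower limits for the -1 and 0 rules come from this model.
3. Add screening IPSS as a second covariate if it is a separate assessment; otherwise leave it out. Do not substitute the mean of the two scores.

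The target difference, margins and test levels stay as they are. No patient, visit or questionnaire is added. The cost is a few sentences in the SAP and one model degree of freedom, or two with the screening score.

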Trial grouping and medication	
According to the random sequence generated by computer, eligible patients were randomly assigned to three groups according to 1: 1: 1.
 
Group A: Tamsulosin combined with Ningmitai Capsules placebo. Oral Tamsulosin Hydrochloride Capsules (each 0.2mg), 1 capsule per time, 1 time a day. Oral Ningmitai Capsules placebo (each 0.38g), 4 capsules per time, 3 times a day. Continuous medication for 12 weeks.
 
Group B: Silodosin Capsules combined with Ningmitai Capsules placebo. Oral Silodosin Capsules (each 4mg), 1 capsule per time, 2 times a day. Oral Ningmitai Capsules placebo (each 0.38g), 4 capsules per time, 3 times a day. Continuous medication for 12 weeks.
 
Group C: Silodosin Capsules combined with Ningmitai Capsules. Oral Silodosin Capsules (each 4mg), 1 capsule per time, 2 times a day. Oral Ningmitai Capsules (each 0.38g), 4 capsules per time, 3 times a day. Continuous medication for 12 weeks.

Combined medication	
Combination drugs banned during the study:
 
 (1) CYP3A4 inhibitors (eg. Ketoconazole, Clarithromycin, Itraconazole, Ritobuvir) (2) Other α-receptor blockers besides this study and other drugs with therapeutic effects on BPH include 5-α reductase inhibitors, phosphodiesterase type 5 (PDE-5) inhibitors, M receptor blockers, β3 receptor agonists, botanical drugs or traditional Chinese medicines, etc. 
Combination drugs used with caution during the study:
 
 (1) Strong inhibitors of CYP2D6 (such as Paroxetine) may lead to a significant increase in exposure to Tamsulosin. (2) Potential P-glycoprotein (P-gp) inhibitors (such as Cyclosporin), in vitro studies have shown that Silodosin is a P-gp substrate, and the inhibition of P-gp may lead to an increase in the blood concentration of Silodosin. (3) Antihypertensive drugs, there is a decline in blood pressure regulation ability when standing up and pay close attention to blood pressure changes when combined with α-receptor blockers. (4) Drugs that may induce or aggravate urinary retention, such as Anticholinergic Atropine, Antiallergic Chlorpheniramine, Antidepressant Imipramine, and ready-for-use traditional Chinese

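### Centre appears in no planned analysis, and the allocation text does not say whether the list was stratified by centre: a modest, avoidable loss of precision in both primary IPSS comparisons

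*Protocol*

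**What the plan says.** The protocol summary (Research design) describes "A multicenter, prospective, randomized, controlled clinical trial design". It lists 8 centres and 312 men, a total that allows for 20% dropout.

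The allocation method is given under Trial grouping and medication, and repeated in the SAP's copy of the summary table: from a computer-generated random sequence, "eligible patients were randomly assigned to three groups according to 1: 1: 1". No block, stratum or per-centre list is mentioned, and none is ruled out.

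The SAP does not name centre anywhere in its analysis text:

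- **Primary endpoint** (section 2(3)①): "the difference of IPSS score decline and 97.5% CI of the three groups were calculated". No model or covariate is given. Silodosin against tamsulosin is tested for non-inferiority with a margin of 1 IPSS point. The combination against silodosin alone is tested for superiority. Each test is at one-sided 0.025 (section 2(1)).
- **Secondary endpoints** (section 2(3)②): one-way analysis of variance or a rank sum test for Qmax, PVR, PSA and prostate volume, and an unstratified chi-square or Fisher test for the proportion improving in severity grade.
- **Cox model for BPH progression** (same section): its factors are not listed.
- **Subgroups**: IPSS severity and NIH-CPSI pain, plus prostatic-fluid leukocytes in the endpoint table. Centre is not among them.

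**The concern.** If mean IPSS change differs between centres, an analysis that ignores centre counts those differences as noise. The interval for silodosin minus tamsulosin and the interval for the combination minus silodosin are then wider than the same data could give. Non-inferiority is judged against 1 point, so interval width matters.

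The choice also has to be made in advance. If centre is added after unblinding, the adjusted result becomes a post hoc choice between two models.

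**Working it through.** **The plan's own figure.** The total of 312 cannot be rederived, because the documents give no SD, expected difference or power. Only the dropout step can be checked: 312 × 0.80 = 249.6, or about 83 evaluable men per arm; 312 / 3 = 104 per arm randomised. (260 × 1.2 also gives 312, so the intended rule is not certain.)

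**Inputs.** From the documents: 8 centres, 104 per arm (83 after dropout), one-sided 0.025, margin 1 point. Assumed: SD of IPSS change 5, equal centre sizes, and an ICC (share of the variance in IPSS change lying between centres) of 0.02 to 0.10.

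**Standard error of an arm difference, unadjusted.** SE = SD × √(2/n).

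- n = 104: 5 × √(2/104) = 0.693
- n = 83: 5 × √(2/83) = 0.776

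**Adjusted for centre, arms balanced within centres.** SE is multiplied by √(1 − ICC). The equivalent gain in patients is 1/(1 − ICC) − 1. A test with 80% power unadjusted has power Φ((0.842 + 1.960)/√(1 − ICC) − 1.960).

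| ICC | SE, n = 104 | SE, n = 83 | Equivalent extra patients | 80% power becomes |
|---|---|---|---|---|
| 0.02 | 0.686 | 0.768 | 2% | 80.8% |
| 0.05 | 0.676 | 0.757 | 5% | 82.0% |
| 0.10 | 0.658 | 0.736 | 11% | 84.0% |

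At 104 per arm the 95% half-width (1.96 × SE) falls from 1.36 to between 1.35 and 1.29 points, a gain of 0.01 to 0.07.

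**If the list ignored centre.** Arms are then unbalanced within centres by chance. Fitting 7 centre terms costs on average 7/(N − 1) of the information: 7/311 = 2.3% at 312 men and 7/248 = 2.8% at 249. The net gain is (1 − 7/(N − 1))/(1 − ICC) − 1. At ICC 0.02 this is −0.3% (N = 312) or −0.8% (N = 249). At ICC 0.05 it is 2.9% or 2.3%. At ICC 0.10 it is 8.6% or 8.0%. The table is therefore the upper end.

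**Simulation check.** Two arms of 83 over 8 centres, 4,000 runs per setting, with a true effect set for nominal 80% power. Power is shown as unadjusted → adjusted:

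| ICC | List ignoring centre | List stratified by centre |
|---|---|---|
| 0.02 | 79.3% → 78.5% | 79.7% → 80.1% |
| 0.05 | 79.8% → 80.2% | 80.1% → 80.7% |
| 0.10 | 79.7% → 81.5% | 81.2% → 83.0% |

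The gains are smaller than the formula's. With two arms only, the 7 centre terms take a larger share (7/165 = 4.2%). Each figure also carries a simulation error of about √(0.8 × 0.2/4000) = 0.6 points.

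Over ICC 0 to 0.10, the unadjusted test's one-sided type I error was 0.019 to 0.026, so there is no inflation above 0.025 beyond simulation error.

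**The case against.** The strongest case against the point is that it is small and rests on assumptions. Neither SD nor ICC is in the documents. At ICC 0.02 the standard error barely moves, and with a list that ignored centre the adjustment can cost as much as it saves. All of that stands, and it limits the point to an inexpensive improvement.

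A reader might also infer more than the documents support:

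- **That allocation was one unstratified list.** This is the natural reading of the wording, but the protocol text is a summary and is silent on blocking and strata. The supportable statement is that the method is not stated.
- **That arms will be badly unbalanced within centres.** With 39 men per centre under simple randomisation, there is a 72% chance that some centre has a gap of 10 or more between some pair of arms. With totals fixed at 104 per arm the figure is 60%, and for one given pair of arms about 30%. Stratification by centre with small blocks would bring it near zero. Unequal head counts do no harm unless centre means differ.
- **That chance imbalance shifts the estimates in addition to widening the intervals.** These are one variance, not two harms. At ICC 0.10 the shift has an SD of 0.693 × √0.10 = 0.219, and 0.658² + 0.219² = 0.693². The unadjusted interval already covers it.
- **That the centres do differ in IPSS administration, visit timing or case mix.** This is plausible, but no passage says so, and entry criteria and visit windows are common to all.

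**Conclusion.** The point holds as an omission with a modest cost. The documents do not say how the sequence handles centre, and no planned analysis names it. Between-centre variation in IPSS change therefore remains in the error term of both primary comparisons. The consequence is lost precision, with no bias and no inflated type I error.

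Under the assumed SD of 5 and ICC of 0.02 to 0.10, the recoverable amount is at most about 2-11% of the sample size, or 1 to 4 power points from a base of 80%. It is less if the list was not stratified. If the list was stratified, an unadjusted test tends to be conservative, so the analysis should still carry the factor.

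**What to change.** Before unblinding, amend SAP section 2(3)① so that both primary IPSS comparisons (Group B minus A for non-inferiority, Group C minus B for superiority) come from one linear model for the change at week 12, with treatment and centre as fixed factors. Add a rule, also fixed before unblinding, for pooling very small centres.

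State in the protocol how the sequence was built: block sizes, any strata, and whether lists were per centre or central. If enrolment has not started, stratify the sequence by centre with permuted blocks; this secures the larger gain shown above. If it has started, keep the list and change only the analysis.

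The cost is about 7 degrees of freedom (8 − 1), a slightly more complex model and, if the list is stratified, somewhat more complex drug supply. No extra patients are needed.
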